10.4. HANDLING OF MISSING DATA

Missing concentration data for subjects who were administered scheduled study treatments will be considered as random non-informative missing for analysis purposes and will not be imputed. Missing values will be examined on a case-by-case basis to confirm this.

- The data will be handled as follows for the graphical presentation of individual plasma concentrations and for the derivation of the PK parameters (using actual sampling times): The time of collection of the pre-dose sample will be set to zero (time 0);
- Actual post-dose sampling times are expressed relative to the time of dosing (if the actual time of sampling is missing, the planned time will be used);
- Pre-dose plasma concentrations below the lower limit of quantification (LLOQ) will be treated as zero for the derivation of PK parameters;
- Concentration values below LLOQ prior to the first quantifiable concentration will be treated as zero for the derivation of PK parameters.
- Post-dose below limit of quantification (BLQ) values after the first quantifiable time point will be set to missing for the derivation of PK parameters.
- For the summary and graphical presentation of plasma concentrations, any plasma concentrations that are BLQ will be treated as zero.
- If all samples are BLQ for a given concentration-time profile, PK parameters will not be derived for that profile.
- No further imputation will be applied to any missing values.

10.5. DATA SUMMARIZATION AND PRESENTATION

PK sample collection data, plasma concentrations and the derived PK parameters for nalbuphine and its metabolites (M1, M3, M4, and M5) will be listed by subject. Plasma concentration data and the PK parameters for the nalbuphine treatments and its metabolites will be summarized by dose level using the following statistics (Table 5):

Table 5 Summary Statistics for PK Analyses

Variable	Summarized with:
Plasma concentration at each time point	n; number of missing (if not zero); number and percent BLQ values; arithmetic mean, SD and coefficient of variation (CV%, calculated as 100*SD/mean); minimum, median and maximum
C _{max} , AUC _{last} , AUC _{inf} , CL/F, Vd/F	n; number of missing (if not zero); arithmetic mean, SD and coefficient of variation (CV%, calculated as 100*SD/mean); minimum, median, and maximum; geometric mean and geometric CV% (calculated as $100\% \times \sqrt{e^{z^2} - 1}$, where z^2 is the variance of the log-transformed data)
t _{max}	n; number of missing (if not zero); median, minimum, maximum, first quartile (Q1) and third quartile (Q3).
t _{1/2} , k _{el}	n; number of missing (if not zero); arithmetic mean, SD and CV (%); minimum, median, and maximum

AUC = area under the curve; BLQ = below the limit of quantification; C_{max} = maximum observed plasma concentration; CV = coefficient of variation; SD = standard deviation; t_{max} = time to maximum plasma concentration; t_{1/2} = terminal elimination half-life; k_{el} = first-order elimination rate constant.

If more than 50% of values are BLQ or are missing, then only n, n (%) BLQ, minimum, median and maximum will be calculated and reported. If the calculated mean/median value is less than LLOQ, then that time point will be ignored for plotting the mean PK profiles.

The following graphical presentations will be made for nalbuphine:

- Mean PK plasma concentrations plotted vs time curve by dose level within the same figure using both linear and log-linear scales.
- Box-whisker plots of PK parameters including C_{max} and AUC_{last} by dose level using linear scale.
- By-subject time-concentration curves by dose level within the same figure using both linear and log-linear scales.

The PK parameters summary will be presented separately for a subset (if applicable) of subjects who do not vomit within 12 hours of dosing.

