### 4.9.2 Dose Escalation and Stopping Rules

Dose escalation may proceed when the DRC have reviewed the available safety data for a cohort (and all preceding cohorts, as applicable) and agree that the safety profile supports proceeding with the evaluation of the next higher dose level. Escalation to the next dose level will continue until the MSD is identified (doses of nalbuphine solution will not exceed 486 mg, which corresponds to 3-fold the therapeutic dose) and only if it is supported by the safety data review by the DRC.

Dose escalation will be stopped if the following is observed in 3 or more subjects who received nalbuphine solution in a cohort experience the following AEs within 4 hours of dosing:

- Grade 3 or higher nausea or,
- Any episode of vomiting or,
- Grade 3 or higher somnolence

Furthermore, dose escalation will be stopped if any of the following is observed in at least 1 subject in a cohort who received nalbuphine solution:

- Sustained (~30 seconds) respiratory depression that results in SpO2 reduction below 92% that requires significant intervention (eg, naloxone administration).
- QTc prolongation (>500 ms or >60 ms above the baseline).
- Any Grade 3 or higher AE or an SAE that is considered by the investigator to be related to nalbuphine and clinically significant, or, any AE deemed by the investigator to be dose-limiting.

If the DRC observe a plateau in the incidence and severity of AEs, which do not meet the stopping criteria described above, then the PK data may be reviewed to determine if there is a plateau in the exposure of nalbuphine despite dose escalation. If a plateau is observed in the PK data, the MSD will be identified based on the available safety and PK exposure data.

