**Table 5 Planned Oral Doses of Nalbuphine Hydrochloride Solution in the Dose Selection Phase**

Cohort (n=8)	Nalbuphine Free Base Dose Level	Nalbuphine HCl Equivalent Dose	Nalbuphine HCl Solution (n=6)	Placebo Solution (n=2)
1	81 mg	90 mg	9 mL × 10 mg/mL + 141 mL flavored beverage	150 mL flavored beverage
2	108 mg	120 mg	12 mL × 10 mg/mL + 138 mL flavored beverage	150 mL flavored beverage
3	135 mg	150 mg	15 mL × 10 mg/mL + 135 mL flavored beverage	150 mL flavored beverage
4	162 mg	180 mg	18 mL × 10 mg/mL + 132 mL flavored beverage	150 mL flavored beverage
5	243 mg	270 mg	27 mL × 10 mg/mL + 123 mL flavored beverage	150 mL flavored beverage
6 a	up to 365 mg	up to 405 mg	up to 40.5 mL × 10 mg/mL + 109.5 mL or required volume of flavored beverage for a total volume of 150 mL solution	150 mL flavored beverage
7 a	up to 486 mg	up to 540 mg	up to 54 mL × 10 mg/mL + 96 mL or required volume of flavored beverage for a total volume of 150 mL solution	150 mL flavored beverage

HCl=hydrochloride.

aThe dose of nalbuphine free base in Cohorts 6 and 7 may increase up to a 50% increase from the preceding dose but not to exceed 486 mg (3-fold the therapeutic dose) based on the evaluation of safety data in the previous cohorts.

For the nalbuphine solution, the dose will be added to a flavored beverage to prepare a dosing solution of 150 mL. For both nalbuphine and placebo treatments, after subjects drink the 150 mL dosing solution, an additional 50 mL of flavored beverage will be added to the dosing container as a rinse and then administered to the subjects. Dosing procedures will be specified in study specific procedures.

Actual doses may be adjusted according to the evaluation of safety data from Part A. Dose reductions, intermediate doses, or higher doses up to 50% greater than the dose administered in the previous cohort may be considered based on the safety results obtained in previous cohorts. Additional cohorts of subjects may be added until the MSD is identified or until lack of linearity is observed in the nalbuphine plasma PK profile (see Section 4.9 for details).

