The dose escalation scheme in Part A was amended to allow an incremental increase in the dose of nalbuphine based on a percentage of up to 50% from the last dose (rather than an absolute 27 mg dose increase), if supported by the safety data of the preceding cohorts.

The amendment is proposed based on the safety results of the first 4 cohorts indicating a lower than expected incidence of AEs and severity up to the 162 mg nalbuphine. Data indicated that - unlike healthy subjects- nalbuphine is much better tolerated in the non-dependent recreational opioid population and that the dose-AE response was flat over the selected dose range. At the 162 mg therapeutic dose (Cohort 4) only one Grade 2 AE was observed out of a total of 14 AEs. Subjects dosed at 81 mg had very mild AEs (2 out of 6 subjects had Grade 1 somnolence) with no nausea or vomiting compared to 5.9% in healthy subjects. Grade 1 vomiting and nausea were observed in one subject out of 6 at 135 mg while doubling the dose from 81 mg to 162 mg resulted in a single AE of Grade 2 nausea reported in one out of 6 drug treated subjects. This is in contrast to the observed incidence of vomiting (32%), nausea (41%) AEs in healthy subjects at the 162 mg dose. There was no effect on oxygen saturation ( $spO_2 > 95\%$ ), ECG parameters, or any other vital signs over 24 hours post-dose in any individual subject up to 162 mg dose.

In view of the “flat” dose-response observed in this subject population, the protocol was amended to allow an incremental increase in the dose of nalbuphine based on a percentage of up to 50% from the previous dose (rather than an absolute 27 mg dose increase). The 50% increase was selected to ensure a sufficient differentiation between the doses while keeping in perspective the potential safety of the subjects as the doses are escalated to the higher doses. Given the high inter-subject variability of 54% in nalbuphine plasma  $C_{max}$  and 46% in AUC, a 50% increase seemed further justified.

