In addition, an option to use both PK and safety data to identify the MSD was included to reduce the potential unnecessary exposure to escalating doses of study drug in the study population. Nalbuphine exposure increases with increasing dose in a proportional fashion over the 27 mg to 162 mg doses, the highest tested dose in healthy subjects. On the other hand, PK in the uremic pruritus subjects on hemodialysis indicated a plateau in exposure when the dose was increased from 162 mg to 216 mg (mean  $C_{max} = 83 \text{ ng/mL}$  and  $AUC = 761 \text{ h}\cdot\text{ng/mL}$  compared to  $80 \text{ ng/mL}$  and  $770 \text{ h}\cdot\text{ng/mL}$ , respectively) (Study TR01). Therefore it would be reasonable to assume that as doses of nalbuphine increase, the exposure in the current otherwise healthy subjects would also start to deviate from proportionality and/or plateau at doses higher than 162 mg. If this were to be the case, then further increases in doses would not be expected to have a significant impact on the safety or tolerability of the drug.

Thus the option to review the PK data to determine if a plateau in the exposure of nalbuphine is reached despite dose escalation was added in Section 4.9.2. Dose Escalation and Stopping Rules. If a plateau is observed in the PK data, the MSD will be identified based on the available safety and PK exposure data. This option is intended to reduce the potential unnecessary exposure to escalating doses of study drug in the study population.

The proposed amendment for the dose escalation will involve at least a Cohort 5 at a dose of 243 mg dose ( $1.5 \times 162 \text{ mg}$ ). As per the amended protocol, the option to dose additional cohorts may be considered proposed if the stopping rules in Section 4.9.2 are not met in Cohort 5.

Typically, human abuse liability studies evaluate the highest proposed therapeutic dose of the test drug as well as doses that are multiples of the highest proposed therapeutic dose (usually 2-3 times greater, if this can be done safely) in comparison to a positive control(s) and placebo. Our intent is to increase the dose until a 2- to 3-fold the therapeutic dose is reached assuming the dose stopping rules are not met. Doses are not to exceed 486 mg (3-fold the therapeutic dose). Figure 1 and Table 5 have been updated accordingly in the protocol to clarify the planned dose escalation scheme.

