3. STUDY OBJECTIVES

3.1. EXPLORATORY OBJECTIVES

The exploratory objectives that will be evaluated in the Dose Selection Phase (referred to as Part A in the Protocol) are the following:

- To assess the safety and tolerability of various doses of orally-administered nalbuphine solution and determine the maximum safe dose (MSD) in non-dependent, recreational opioid users.
- To assess the PK and pharmacodynamics (PD; pupillometry) of various doses of orally-administered nalbuphine solution in non-dependent, recreational opioid users.

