For the nalbuphine solution, the dose will be added to a flavored beverage to prepare a dosing solution of 150 mL.

For both nalbuphine and placebo treatments, after subjects drink the 150 mL dosing solution, an additional 50 mL of flavored beverage will be added to the dosing container as a rinse and then administered to the subjects. Dosing procedures will be specified in study specific procedures.

[figure not shown]
Actual doses may be adjusted according to the evaluation of safety data. Dose reductions, intermediate doses, or higher doses up to 50% greater than the dose administered in the previous cohort may be considered based on the safety results obtained in previous cohorts. Additional cohorts of subjects may be

added until the MSD is identified, or until lack of linearity is observed in the nalbuphine plasma PK profile (see Section 4.9 of the Protocol for details).

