4.1.3. Exploratory Endpoints

The exploratory endpoints for this study are:

- Identification of a MSD of nalbuphine administered as nalbuphine oral solution.

- Concentration-versus-time profiles of nalbuphine in plasma and PK parameters C_{\max} , t_{\max} , and AUC_{last} . If data allow then the PK parameters AUC_{inf} , k_{el} , $t_{1/2}$, CL/F and Vd/F will be calculated.
- Pupillometry (maximum pupil constriction [MPC], time to MPC [TMPC], and time-averaged pupillometry area over the curve [TA_PAOC]).

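### SAP 10.5 plans no dose-exposure estimate with an interval, a gap mainly for Cmax, although a PK plateau may inform the maximum safe dose

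*SAP*

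**What the plan says.** SAP 10.5 lists PK data by subject and says that "Plasma concentration data and the PK parameters for the nalbuphine treatments and its metabolites will be summarized by dose level using the following statistics". Its Table 5 gives n, mean, SD, CV, median and range, plus geometric mean and geometric CV for Cmax, AUClast, AUCinf, CL/F and Vd/F. The planned figures are mean and individual concentration curves and linear-scale box plots of Cmax and AUClast by dose. A separate PK parameter summary is planned for subjects who do not vomit within 12 hours. The table and figure indexes (SAP 15 and 17) add no dose-exposure estimate, and protocol 8.1.4 is also descriptive.

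Elsewhere the shape of exposure against dose has a role:

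- Protocol 4.9.2, after an optional PK review prompted by a plateau in adverse events: "If a plateau is observed in the PK data, the MSD will be identified based on the available safety and PK exposure data".
- The notes to protocol Table 5 allow cohorts to be added until the MSD is identified, "or until lack of linearity is observed in the nalbuphine plasma PK profile". SAP 3.6 repeats this and sends the reader elsewhere for the detail: "lack of linearity is observed in the nalbuphine plasma PK profile (see Section 4.9 of the Protocol for details". Protocol 4.9 neither uses nor defines that term, and gives no numerical meaning for a plateau.
- Protocol 12.2 (Amendment 2) records the sponsor's expectation that exposure "would also start to deviate from proportionality and/or plateau at doses higher than 162 mg".
- SAP 3.1 makes it an objective "To assess the PK and pharmacodynamics (PD; pupillometry) of various doses of orally-administered nalbuphine solution", and SAP 4.1.3 keeps as an endpoint "Identification of a MSD of nalbuphine administered as nalbuphine oral solution".

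**The concern.** The sponsor stated an expectation about how exposure behaves above 162 mg and gave that behaviour a possible part in identifying the MSD. No planned output estimates it with an interval. A reader of the report would judge any plateau by comparing geometric means between cohorts of 6. Those means are imprecise, so a flat-looking step can arise by chance, and a real flattening can be hidden.

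What is at stake is limited to how well the MSD report, and the PK support for the Part B dose choice, can be read. Under protocol 4.9.1 the Data Review Committee considers Part A results when choosing Part B doses, and SAP 5 says Part B is still to be placed at a new site.

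**Working it through.** **The plan's own figures.** No precision figure for proportionality or plateau is stated, so there is none to reproduce. The dose arithmetic agrees: 1.5 × 162 = 243, 1.5 × 243 = 364.5 (given as up to 365), 3 × 162 = 486 mg. The healthy-subject means in protocol 1.1 (27 to 162 mg) imply slopes of ln(21.6/4.13)/ln 6 = 0.92 for Cmax and ln(328/58.8)/ln 6 = 0.96 for AUC, in line with the protocol's description of near-proportional exposure.

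**Inputs.**
- 6 active subjects per cohort (SAP 3.2).
- Doses 81, 108, 135, 162, 243, then up to 364.5 and 486 mg (SAP Table 1).
- CV from protocol 12.2: "Given the high inter-subject variability of 54% in nalbuphine plasma" Cmax, and 46% for AUC. The source study is not named. I assume these apply to the solution in this population and show Cmax results for CV 40 to 65%.
- Log-normal data, with every active subject evaluable.

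**Step 1, log-scale SD.** SD = √ln(1 + CV²) = √ln(1 + 0.54²) = 0.506.

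**Step 2, two adjacent cohorts.** SE = 0.506 × √(2/6) = 0.292. With 10 df, t = 1.812, so the 90% CI factor is exp(1.812 × 0.292) = 1.70 (range 1.50 to 1.86). At the AUC CV of 46%, SE = 0.253 and the factor is 1.58. Both exceed the 1.5-fold dose step.

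**Step 3, chance of a flat step under true proportionality.** Φ(−ln 1.5 / 0.292) = Φ(−1.39) = 8.3% for 162 to 243 mg (3.4 to 11.8%). By simulation, at least one flat or falling step over 162, 243 and 364.5 mg occurs 16.5% of the time (6.8 to 23.6%). These are chances of a flat-looking step, not of a wrong stop.

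**Step 4, what CL/F already shows.** CL/F = dose/AUCinf (SAP 10.3). Proportional AUC leaves it constant; AUC flat from 162 to 243 mg would raise it 1.5-fold. Assuming the 46% CV holds for AUCinf, a CL/F ratio between two cohorts carries the 1.58 factor from Step 2, and no interval is planned for it. It says nothing about Cmax.

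**Step 5, pooled slope.** In ln(Cmax) = a + b·ln(dose), SE(b) = SD/√Sxx, where Sxx = 6 × Σ(ln dose − mean ln dose)². For five cohorts Sxx = 4.135, SE = 0.506/√4.135 = 0.249, and the 90% half-width is 1.701 × 0.249 = 0.42. The last two columns give the simulated probability that the upper 90% limit falls below 1, at CV 54%.

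| Doses fitted (mg) | n | Sxx | SE | 90% half-width (CV 40–65%) | Expected slope if flat above 162 | Upper limit <1, flat above 162 | Upper limit <1, slope 0.5 above 162 |
|---|---|---|---|---|---|---|---|
| 81–243 | 30 | 4.135 | 0.249 | 0.42 (0.32–0.50) | 0.66 | 37% | 16% |
| 81–364.5 | 36 | 8.996 | 0.169 | 0.29 (0.22–0.34) | 0.44 | 94% | 48% |
| 81–486 | 42 | 15.326 | 0.129 | 0.22 (0.17–0.26) | 0.34 | >99% | 80% |
| 162–364.5 | 18 | 1.973 | 0.360 | 0.63 (0.48–0.74) | 0 | 84% | 38% |
| 162–486 | 24 | 4.135 | 0.249 | 0.43 (0.32–0.50) | 0 | 99% | 62% |

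If exposure is proportional throughout, the upper limit falls below 1 about 5% of the time in every fit.

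**The case against.** The strongest case against is that nothing promised is missing. The objective is to assess PK, the named endpoints are profiles and parameters, and protocol 8.1.4 is descriptive too. That stands: this is an improvement, not a breach of the protocol.

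It is also fair that CL/F by dose is a planned, dose-normalised output, and that the slope could be worked out by hand from the planned geometric means and CVs. A reader might infer that the SAP offers no view of proportionality at all; that goes too far. What remains is the missing interval, and Cmax.

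The committee's reasoning is to be documented (protocol 3.1.2), and its dose-selection decisions go in the study report appendix (protocol 8.1.6). That preserves the rationale but supplies no estimate.

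A reader might infer from Step 3 that escalation was stopped by chance or that the MSD is unsound. The documents do not support this. PK review was optional, followed an adverse-event plateau, and was not the basis for escalation (protocol 3.1.2). Part B doses rest mainly on safety (protocol 5.4.1). Nothing shows that the PK route was used, or which doses were actually given after the fourth cohort.

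Two technical objections also stand. A straight log-log line is the wrong shape for exposure that rises and then flattens, so a slope below 1 is not evidence of a plateau. And if vomiting of the oral solution becomes more common with dose, lost drug would pull the slope below 1. The fix has to respect both.

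**Conclusion.** The point holds as a low-cost improvement worth considering. SAP 10.5 leaves the dose-exposure relation to by-dose description: CL/F covers AUC indirectly and without an interval, and Cmax is not covered. At the stated Cmax CV a comparison of two cohorts is uncertain by a factor of 1.70, whereas a slope pooled over 5, 6 or 7 cohorts has a 90% half-width of 0.42, 0.29 or 0.22.

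The gain depends on the doses given. If they stopped at 243 mg, the slope would show less-than-proportional exposure only about 37% of the time even with exposure completely flat above 162 mg. The higher probabilities need cohorts 6 and 7, dosed at their planned maximum. All figures assume 6 evaluable subjects per dose, log-normal data and that the quoted CV applies here. The analysis bears on reporting and on support for Part B, not on the completed escalation.

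**What to change.** Add to SAP 10.5:

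- A power model of ln(Cmax) and ln(AUClast) on ln(dose) across all nalbuphine cohorts in the Dose Selection PK Population.
- The same model for 162 mg and above, where at least three such cohorts exist.
- A repeat in the already planned subset without vomiting within 12 hours of dosing.
- Slopes with 90% CIs, shown beside the by-dose CL/F summary, for the MSD report and the Part B dose choice.
- A label saying the analysis is supportive and was added after Part A was completed.
- A reading rule: an upper limit below 1 means less-than-proportional exposure, not a plateau, and is read with the non-vomiter result. Set no pass/fail criterion.

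Protocol 4.9.2 need not change. The cost is a few regressions on data already collected and one table. The downside is a possibly inconclusive result: with data only to 243 mg the fit from 162 mg upward is not run, and the overall Cmax slope is known only to about ±0.42.

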11. SAFETY

All safety analyses will be done using the Dose Selection Safety Population.

11.1. EXTENT OF EXPOSURE

Drug administration data for the Dose Selection Phase will be listed for the Dose Selection Randomized Population.

11.2. TREATMENT COMPLIANCE

Not Applicable (NA).

11.3. ADVERSE EVENTS / ADVERSE DRUG REACTIONS

Analysis of safety assessments will be performed using the Dose Selection Safety Population. Assessment of safety will be based on the incidence of AEs, AEs resulting in discontinuation, and SAEs by treatment. AE summaries will be provided showing the number and percentage of subjects who experienced at least one TEAE. TEAEs will also be tabulated by maximum severity and by maximum relationship to study drug. These summaries will be presented by body system and PT (MedDRA, version 20.0 or higher). SAEs and AEs resulting in discontinuation will be summarized separately. All AEs will be listed by subject for the Dose Selection Randomized Population.

Any AE occurring after treatment start will be considered as a TEAE. Rules related to assigning TEAEs to treatment and imputation related to missing data are described in the Section 7.3.

Subjects may be counted under multiple system organ classes (SOCs) and PTs, but for each SOC and PT, subjects are only counted once.

The number and percentages of subjects with TEAEs as well as the number of events will be displayed. SOC's will be sorted by descending frequency of subjects. Within each SOC the PTs will be sorted by descending frequency of subjects.

Imputation related to missing AE data is described in the Section 7.3.

